2.0 BACKGROUND INFORMATION AND RATIONALE

Metastatic melanoma historically has had a very poor survival. Thankfully this is now changing due to advent of new targeted drugs and breakthroughs in immunotherapy. Programmed cell death 1 (PD-1) receptor is an inhibitory receptor expressed by T cells. Its ligand, PD-L1 is frequently expressed within the tumour microenvironment including tumour cells. Tumour models have shown that PD-1 negatively regulates the effector phase of T-cell responses after ligation of PD-L1 expressed within the tumour [Blank 2004]. Several drugs have been developed that block PD-1 and hence augment the T cell response. The most mature results have been obtained in advanced melanoma patients and indicate high response rates, high quality responses and prolonged duration of response and prolonged survival.

Pembrolizumab is a highly selective, humanized monoclonal IgG4-kappa isotype antibody against PD-1 that is designed to block the negative immune regulatory signalling of the PD-1 receptor expressed by T cells [Hamid 2013]. Pembrolizumab has shown improved response rates, response duration and survival compared to standard treatments for melanoma [Ribas 2015; Patnaik 2014]. Patients receiving pembrolizumab had an overall RR of 38% with durable responses and approximately a further 30% of patients with disease control. The 1 year survival in this trial was 67% and 50% at 2 years in patients with metastatic melanoma [Daud 2015]. Pembrolizumab was also compared to ipilimumab in first line therapy for metastatic melanoma and showed a better RR and OS rate compared to ipilimumab with a RR of 34% compared to 12% and OS at 12 months of 74% compared to 58% for ipilimumab [Robert 2015]. In this study and subsequent phase III studies, pembrolizumab is administered intravenously at 2 mg/kg every 2 weeks for a total of 2 years. Recent results from pharmacokinetic studies indicate that a flat dose of 200 mg IV is sufficient for exposure and that there is no additional advantage to weight-based dosing. In addition, responses occur early within the first 8 weeks and it is possible that 2 years of consecutive therapy may not be needed given the durable responses seen with ipilimumab short courses.

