9.1 Evaluation During Protocol Treatment

	Investigations	Timing
History and Physical Exam including:	
 history weight ECOG Performance status vital signs (blood pressure and pulse) clinical tumour measurements (if applicable) 	Day 1 each cycle
Hematology*	
 CBC, differential, platelets 	Day 1 each cycle
Biochemistry*	
 electrolytes (sodium, potassium, chloride, bicarbonate) alkaline phosphatase AST, ALT serum creatinine bilirubin 	Day 1 each cycle
	
 phosphorous calcium magnesium albumin 	As clinically indicated
	
 TSH, FT3, FT4 	Every other cycle
Radiology**	
 CT scan with contrast of chest, abdomen/pelvis Other sites as clinically indicated 	4 weeks, 12 weeks, then every 12 weeks
Other Investigations	
 ECG 	As clinically indicated
Economics	
 Health Utilities Index (EQ-5D) Resource Utilization Assessment 	To be completed at each 12 weekly visit until progression OR maximum 1 year from registration
Adverse Events***	Patients must be evaluated after each cycle for adverse events	

* Bloodwork Timing: Pre-treatment blood draws should be done within 72 hours (maximum) prior to treatment.

** Patients with a CR or PR should have scans repeated after minimum 4 weeks to confirm response. See Appendix VII for CT requirements.

*** Adverse events will be recorded and graded according to the NCI Common Terminology Criteria for Adverse Events (CTCAE) (Appendix V).

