14.4 Economic Analysis

The purpose of the CCTG economic evaluation in this phase II study is to determine the incremental cost-effectiveness and cost-utility of pembrolizumab from a universal access government payer perspective, over a lifetime time horizon by prospectively collecting resource utilization information during this clinical trial and comparing to data collected from public databases.

In this study, a cost-utility analysis will be conducted to compare the overall cost per quality-adjusted-life-year (QALY) for pembrolizumab individually with dacarbazine and ipilimumab. Case report forms will be used in this study to document non-protocol based health care resource utilization over the course of treatment and follow-up, including outpatient consultations/visits/investigations, inpatient admissions, emergency room visits, supportive care medication for management of toxicity, and investigations/admissions/treatment of adverse events and disease progression. Forms will be ascertained at 12-week intervals while on treatment until disease progression or a maximum period of 12 months. Unit costs for drugs, hospitalizations, and treatments will be ascertained using publically available sources and reported in adjusted Canadian dollars.

Patient preferences while on pembrolizumab, or utilities, will be derived from the EQ-5D questionnaire [*Brooks 1996; Drummond 1997; www.euroqol.org*]. The EQ-5D self-administered questionnaire consists of two pages comprising the EQ-5D descriptive system and the EQ VAS. The EQ-5D descriptive system comprises five dimensions of health (mobility, self-care, usual activities, pain/discomfort, anxiety/depression) and each dimension comprises three levels (no problems, some/moderate problems, extreme problems). The five level score may also be used. A unique EQ-5D health state is defined by combining one level from each of the five dimensions. The EQ VAS records the respondent's self-rated health status on a vertical graduated (0-100) visual analogue scale. The EQ-5D is a validated instrument that has been used in population surveys and clinical trial settings. EQ-5D will be obtained at prescribed intervals. Utilities for patients on dacarbazine and ipilimumab will be obtained from published literature [*Tomme 2014*].

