APPENDIX I - PATIENT EVALUATION FLOW SHEET

Required Investigations	Pre-study (within 7 days prior to registration, or as noted)	Day 1 each cycle	As clinically indicated	Every 12 weekly visit	4 wks, 12 wks then every 12 weeks	4 Weeks post treatment
History & Physical Exam						
Height and Weight	X ¹	X				X
ECOG Performance Status	X ¹	X				X
Vital signs (blood pressure and pulse)	X ¹	X				X
Documentation of all measurable and non-measurable disease	X ¹				X	X (if applicable)
Clinical tumour measurements (if applicable)	X ¹	X			X	X (if applicable)
Hematology & Biochemistry²						
CBC, differential, platelets	X	X				X
Serum creatinine, sodium, potassium, chloride, bicarbonate, bilirubin, ALP, AST, ALT, LDH ³ ,	X	X				X
Phosphorous, calcium, magnesium, albumin	X		X			
TSH, FT3, FT4	X	X ⁴				
HCV, HBV screening serology (if unknown)	X					
Other Investigations						
Pregnancy test, in women of childbearing potential only	X					
ECG	X ⁵		X			
Economics						
Health Utilities Index (EQ-5D)	X			X ⁶		
Resource Utilization Assessment				X ⁶		
Radiology						
CT scan with contrast of chest, abdomen/pelvis Other sites as clinically indicated	X (within 28 days prior to registration; 35 if negative)				X ⁷	X ⁸
Adverse Events						
Adverse Events/ Baseline Symptoms ⁹	X			Continuously each visit		X
1 Within 14 days prior to registration.						
2 Bloodwork Timing: Pre-treatment blood draws should be done within 72 hours (maximum) prior to treatment.						
3 LDH is not required after baseline.						
4 Every other cycle						
5 Only required if not done within 6 months prior to registration						
6 Each 12 weekly visit until progression OR maximum 1 year from registration						
7 Patients with a CR or PR should have scans repeated after minimum 4 weeks to confirm response						
8 All patients will be seen at 4 weeks after the end of last cycle date. Thereafter, continued follow-up is not required for patients who go off protocol treatment with progressive disease, except to document ongoing toxicities (until resolved to \leq grade 2) and late toxicities (including second malignancies). For patients who go off protocol therapy before progression is documented or have objective CR, PR or SD ongoing, follow-up and a Follow-up Report will be required at least every 3 months for a maximum of 1 year. A Death Report will be required for all patients.						

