APPENDIX IV - DOCUMENTATION FOR STUDY

Follow-up is required for patients from the time of registration and will apply to all eligible and ineligible patients. This trial will use a web-based Electronic Data Capture (EDC) system for all data collection including SAE reporting (see section 11.0 for details regarding SAE reporting). For details about accessing the EDC system and completing the on-line Case Report Forms, please refer to the Data Management Guidebook posted on the IND.225 area of the CCTG web-site (www.ctg.queensu.ca).

Form	To be Completed/Submitted Electronically:	Supporting Documentation to be sent using Supporting Document Upload Tool ²
PATIENT ENROLLMENT FOLDER	Must be completed at time of registration to confirm eligibility.	
BASELINE REPORT	Due within 2 weeks of patient registration.	Copies of signed consent signature page(s); relevant pathology and radiology reports; ECG reports
TREATMENT REPORT	To be completed every 3 weeks (i.e. after each cycle). Due within 2 weeks of end of cycle. This form documents treatment, adverse events, investigations and response assessment for each cycle.	Relevant radiology reports.
HEALTH UTILITIES INDEX (EQ-5D)	To be completed within 7 days prior to registration and at each 12 weekly visit until progression OR maximum 1 year from registration	Relevant radiology reports.
RESOURCE UTILIZATION ASSESSMENT	To be completed at each 12 weekly visit until progression OR maximum 1 year from registration.	Relevant radiology reports.
END OF TREATMENT REPORT	To be completed when patient goes off protocol treatment. Due within 2 weeks of end of protocol treatment.	
4 WEEK POST TREATMENT REPORT	To be completed once on all patients, 4 weeks after going off protocol treatment. Due within 2 weeks after contact with patient.	
FOLLOW-UP REPORT	Continued follow-up is not required for patients who go off protocol treatment with progressive disease , except to document ongoing toxicities (until resolved to \leq grade 2) and late toxicities (including second malignancies). For patients who go off protocol therapy before progression is documented or have objective CR, PR or SD ongoing, follow-up and a Follow-up Report will be required every 3 months for a maximum of 1 year. Due within 2 weeks after contact with patient.	Relevant radiology reports.

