Health utilities data are collected for research purposes, and will not be used for the patient's individual medical care. The assessment is in the form of a self report questionnaire. Therefore, it must be completed by the patient only, without translation, coaching or suggestions as to the “correct” answer by relatives or health care personnel.

The usual scheduled times to obtain the questionnaires are as follows:

- Pre-registration (for this study, within 7 days prior to registration)
- During treatment (for this study, at each 12 weekly visit until progression OR maximum 1 year from registration)

The information provided by the patient in the completed questionnaire is confidential and should not be discussed with or shown to anyone who is NOT mentioned in the consent form signed by the patient.

If a particular question has not been answered, please document the reason(s) in the appropriate space on the questionnaire. If the whole questionnaire has not been completed, please document the reason(s) on the appropriate case report forms.

2. Pre-treatment Assessment

It should be explained to the patient that the purpose of the questionnaire is to assess the impact of treatment on different areas of the patient's life, eg: psychological distress, social disruption, symptoms, side effects, et cetera.

The Clinical Research Associate (CRA) should collect the questionnaire as soon as it has been completed, check to see that each question has been answered and gently remind the patient to answer any inadvertently omitted questions. If a patient states that s/he prefers not to answer some questions and gives a reason(s), the reason(s) should be noted on the questionnaire. If a specific reason is not given, this also should be noted on the questionnaire.

3. Assessments During Treatment

The health utilities questionnaire should be given to the patient before being seen by the doctor, and prior to treatment on the day of treatment, as required by the schedule in the protocol. If the patient does not have a doctor visit scheduled, or if it was not possible for the patient to complete the questionnaire before being seen by the doctor, s/he should still complete the questionnaire prior to treatment.

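### Economics forms fall only on 12-weekly visits, with none on leaving treatment, and the stop rules differ, so early leavers give no resource-use form and no on-treatment EQ-5D

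*Combined protocol and SAP*

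**What the plan says.** Post-baseline EQ-5D and Resource Utilization forms are tied to 12-weekly visits wherever they appear. The EQ-5D also has a baseline form; resource use does not.

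- Section 14.4, on the resource-use forms: "Forms will be ascertained at 12-week intervals while on treatment until disease progression or a maximum period of 12 months". The same section says the forms are to "document non-protocol based health care resource utilization over the course of treatment and follow-up".
- Section 9.1, the on-treatment table, and Appendix IV, for resource use: "To be completed at each 12 weekly visit until progression OR maximum 1 year from registration".
- Appendix IV, for the EQ-5D: "To be completed within 7 days prior to registration and at each 12 weekly visit until progression OR maximum 1 year from registration".
- Appendix I, footnote 6: "Each 12 weekly visit until progression OR maximum 1 year from registration". Its economics rows have no mark in the column for 4 weeks post treatment.
- Appendix VII, for the EQ-5D: "During treatment (for this study, at each 12 weekly visit until progression OR maximum 1 year from registration".
- Section 9.2 requires every patient to be seen 4 weeks after the end of the last cycle, and patients off treatment without progression to be followed at least every 3 months for up to 1 year. Its table has no economics row.

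CT scans are due at "4 weeks, 12 weeks, then every 12 weeks" (Section 9.1), so disease is first reassessed 8 weeks before the first economics form.

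**The concern.** Cost per QALY against dacarbazine and against ipilimumab makes up two of the secondary objectives in Section 1.2. The Markov model in Section 14.4 takes pembrolizumab costs from this trial and multiplies life-years by time-weighted utilities.

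Under the schedule, whether a patient contributes any post-baseline economic data depends on how the patient fares. Those who progress, die or stop early are plausibly the ones with more admissions and lower utility, and they contribute least. The progression-free state would then be costed and valued mainly from patients who stayed on. Section 14.4 states no method for missing economic data. It names hospitalizations, drug costs and survival for the 20% variation in either direction, but not utilities.

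The differing stop rules add a second problem. After a stop without progression, sites cannot tell whether forms are still due. This point is about time before progression; the absence of forms after progression is a separate matter.

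**Working it through.** The plan gives no figure to reproduce here. The check counts forms and then illustrates the size of the gap.

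**1. Visit grid.** With a 12-week interval and a 1-year limit, forms fall at weeks 12, 24, 36 and 48: four forms. With 3-week cycles (Section 8.1), doses are due at weeks 0, 3, 6 and 9 before the first form. Progression before week 12 therefore gives 0 resource-use forms and 0 on-treatment EQ-5Ds under every version of the rule.

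**2. Stop rules side by side.** All versions share the limit of progression or about 1 year. Section 14.4 adds that the patient is on treatment. Section 9.1 and Appendix VII carry an on-treatment heading and can be read the same way. Appendices I and IV carry no such condition.

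**3. Stop without progression, then progression-free to 1 year.**

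| Stop at week | Forms, on-treatment reading | Treated weeks since last form | Forms, Appendix I/IV reading |
|---|---|---|---|
| 9 | 0 | 9 | 4 |
| 20 | 1 | 20 − 12 = 8 | 4 |
| 26 | 2 | 26 − 24 = 2 | 4 |
| 40 | 3 | 40 − 36 = 4 | 4 |

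**4. Share affected (assumption).** The documents do not give the share leaving before week 12. Section 2.0 cites an earlier pembrolizumab trial with an "overall RR of 38% with durable responses and approximately a further 30% of patients with disease control". That leaves 1 − 0.38 − 0.30 = 0.32 without disease control, which serves as an upper illustration. The lower end, 10%, has no source in the documents. Of 80 evaluable patients, these shares are 8 and 25.6 (about 26).

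**5. Non-drug cost, first 12 weeks.** Let f be the share of early leavers. Assume they leave at 6 weeks on average, at twice the weekly non-drug cost of those who stay (rate 2 against 1).

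- Patient-time per patient = 6f + 12(1 − f)
- Cost per patient = 2 × 6f + 12(1 − f) = 12 for every f
- True weekly rate = 12 / patient-time; rate from completed forms = 1

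| f | Patient-time | True rate | Recorded rate too low by |
|---|---|---|---|
| 0.10 | 0.6 + 10.8 = 11.4 | 1.053 | 5% |
| 0.20 | 1.2 + 9.6 = 10.8 | 1.111 | 10% |
| 0.32 | 1.92 + 8.16 = 10.08 | 1.190 | 16% |

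**6. Utility, time-weighted as Section 14.4 specifies.** Assume leavers' utility is 0.15 lower. The bias is their share of patient-time × 0.15:

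- f = 0.10: 0.6 / 11.4 = 0.053; bias 0.008
- f = 0.20: 1.2 / 10.8 = 0.111; bias 0.017
- f = 0.32: 1.92 / 10.08 = 0.190; bias 0.029

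For scale, an assumed SD of 0.20 to 0.25 with n = 80 gives a standard error of 0.20/√80 = 0.022 to 0.25/√80 = 0.028.

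**The case against.** The strongest reply has four parts.

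*Other records exist.* Treatment Reports every 3 weeks record treatment, adverse events and investigations. Serious adverse event reports come with admission and discharge summaries and run to 30 days after the last dose. Every patient has a baseline EQ-5D. This stands in part. A reader might infer that early leavers have no cost data at all, and the documents do not support that: drug exposure and some toxicity cost can be recovered. However, Section 14.4 also wants outpatient visits, emergency visits and supportive medication. Section 11.1 excludes events definitely related to disease from expedited reporting, and does not count palliative or terminal admissions as serious hospitalizations. Those exclusions fall on early failures. A baseline EQ-5D is not a utility on pembrolizumab.

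*The rule conflict is narrow.* This stands. Section 14.4 is not an end-of-treatment rule; it carries the same progression and 12-month limits, and the difference is one added condition. Nor do all toxicity stops lack data: those after week 12 keep their earlier forms, and under Appendices I and IV collection continues.

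*The 32% is not a week-12 departure rate.* This stands. Progression first seen on the week-12 scan coincides with a form visit. Section 10.2.5 lets clinically well patients continue past RECIST progression, with iRECIST confirmation 4 to 8 weeks later. The figure is a ceiling.

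*Sensitivity analysis covers it.* The 5% to 16% lies within the planned 20% variation. Varying symmetrically around a shifted base case does not, however, remove a one-directional error.

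**Conclusion.** The point holds for the schedule gap and for the inconsistent stop rule. Patients who progress before week 12 give no resource-use form and no on-treatment EQ-5D on any reading. Later leavers lose the interval since the last form. Collection after a stop without progression is undefined.

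The size rests on assumptions: 10% to 32% leaving before week 12, at 6 weeks on average, with double the weekly non-drug cost and 0.15 lower utility. Non-drug cost in the first 12 weeks is then 5% to 16% too low and time-weighted utility about 0.008 to 0.029 too high, at most about one of the illustrative standard errors. The utility shift is smaller again once the later progression-free time of those who stay is counted.

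Two stronger readings should be resisted. Weighting utility by headcount (f × 0.15, or 0.015 to 0.048) conflicts with the time weighting in Section 14.4. And a reader might conclude that both cost-effectiveness ratios are too favourable to pembrolizumab; that direction is likely but not shown, since comparator utilities and survival come from literature outside the documents.

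The primary texture objective is unaffected. This is an inexpensive improvement to two secondary objectives, and worth making because resource use and utilities cannot be fully reconstructed later.

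**What to change.** 1. Add a Resource Utilization form at the existing 4-week post-treatment visit for all patients, covering the period since the last form. Record the progression date on it so that cost can be split by health state. For deaths, complete it from the chart.
2. Collect an EQ-5D at the visit where treatment is discontinued. Label any EQ-5D taken after progression as post-progression, so that it is not used as progression-free utility. For the same reason, an EQ-5D at the 4-week visit cannot fill the gap for patients who left because of progression.
3. Use one stop rule in Sections 14.4, 9.1 and 9.2 and in Appendices I, IV and VII: patients off treatment without progression continue 12-weekly forms to progression or 1 year from registration, at the follow-up already required at least every 3 months.

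The cost is one form at a visit every patient already attends, one short questionnaire at discontinuation, chart completion for deaths, and at most the four scheduled form sets for patients off treatment without progression. Site burden is small. The change concerns data collection only. It does not fully recover progression-free utility for patients whose progression is already known when they stop, so Section 14.4 should also state how missing economic data will be handled.

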1.2 Secondary Objectives

- To assess whether tumour texture parameters from a CT scan can correlate with time to disease progression in patients with metastatic melanoma being treated with pembrolizumab.
- To assess duration of response (DoR).
- To assess overall response rate (ORR, PR, CR).
- To assess overall survival (OS).
- To compare cost per quality adjusted life years (QALY) between pembrolizumab and dacarbazine.
- To compare cost per quality adjusted life years (QALY) between pembrolizumab and ipilimumab.
- Toxicity using the CTCAE v.4.

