A decision analytic Markov model will be used to extrapolate the costs and survival estimates from the current study (for pembrolizumab) and dacabazine/ipilimumab in order to generate cost/life-year estimates over clinically plausible scenarios. Survival estimates for dacarbazine and ipilimumab will be obtained from previously published randomized controlled trials [*Robert 2011*]. Life-year estimates will be multiplied by time-weighted utility values to generate QALYs. Use of pembrolizumab will be individually compared with dacarbazine and ipilimumab to generate incremental cost effectiveness ratios (ICERs) expressed as cost/QALY.

Deterministic and probabilistic sensitivity analyses using Monte Carlo simulations will be used to explore the robustness of the model to clinically plausible variations in key assumptions and variations in the analytical methods used. Major drivers of medical care costs, including hospitalizations, drug costs, and survival, will be varied +/- 20% and based on reported estimates provided in the literature. Cost effectiveness acceptability curves will be used to understand the impact of different thresholds of cost effectiveness and increase generalizability of results.

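### Section 14.4 plans two separate pairwise ICERs for three alternative treatments and does not say which one governs the cost-effectiveness conclusion

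*Combined protocol and SAP*

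**What the plan says.** Section 1.2 sets two separate economic objectives: "To compare cost per quality adjusted life years (QALY) between pembrolizumab and dacarbazine" and "To compare cost per quality adjusted life years (QALY) between pembrolizumab and ipilimumab". There is no objective comparing ipilimumab with dacarbazine.

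Section 14.4 keeps that structure. The cost-utility analysis is to "compare the overall cost per quality-adjusted-life-year (QALY) for pembrolizumab individually with dacarbazine and ipilimumab", and the ratios are described the same way: "Use of pembrolizumab will be individually compared with dacarbazine and ipilimumab to generate incremental cost effectiveness ratios (ICERs) expressed as cost/QALY". The analysis is framed "from a universal access government payer perspective, over a lifetime time horizon".

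The modelling covers all three treatments: "A decision analytic Markov model will be used to extrapolate the costs and survival estimates from the current study (for pembrolizumab) and dacabazine/ipilimumab". Utilities for the two comparators come from published literature.

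Deterministic and probabilistic sensitivity analyses are planned, with the main cost drivers and survival varied by 20% either way. On decision uncertainty the plan says: "Cost effectiveness acceptability curves will be used to understand the impact of different thresholds of cost effectiveness". It does not say whether those curves are drawn per pair or over all three treatments.

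Neither section mentions ranking by cost or effect, dominance or extended dominance, net benefit, or which ICER carries the conclusion.

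**The concern.** The trial studies first-line therapy (Section 4.0) in patients with no prior systemic therapy for metastatic disease (Section 5.1.5). Section 2.0 describes a first-line comparison of pembrolizumab with ipilimumab, and Section 14.4 adds dacarbazine as a second comparator. For a single payer these are three alternative ways to start treatment, of which a patient receives one.

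With more than two alternatives, the ratio that informs the choice is the one against the next best option left after dominated and extendedly dominated options are removed. Two ratios calculated separately do not say which of them that is. If a report led with whichever ratio met a threshold, pembrolizumab could be called cost-effective at a threshold where another of the three options gives better value. Because no rule is fixed in advance, the choice of headline would be made after both figures are known.

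**Working it through.** **Inputs.** The documents give no cost, QALY, ICER or willingness-to-pay threshold, so there is no planned figure to reproduce. From the documents come only the two pairwise comparisons (Sections 1.2 and 14.4), the single payer, and the model covering three treatments (Section 14.4). All costs, QALYs and thresholds below are assumed for illustration.

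**Formulas.** Let D = dacarbazine, I = ipilimumab, P = pembrolizumab, with cost C and QALYs Q.
- ICER(X vs Y) = (C_X − C_Y) / (Q_X − Q_Y).
- Net benefit at threshold L: NB_X = L × Q_X − C_X. The best-value option has the largest NB.
- If Q_D < Q_I < Q_P, then ICER(P vs D) = w × ICER(I vs D) + (1 − w) × ICER(P vs I), with w = (Q_I − Q_D) / (Q_P − Q_D). The two planned ratios agree only if I lies on the straight line joining D and P.

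**Case A: ipilimumab is poor value.** D = 20k, 1.0 QALY; I = 120k, 1.3; P = 160k, 2.0.
- P vs I: (160 − 120) / (2.0 − 1.3) = 57,143 per QALY.
- P vs D: (160 − 20) / (2.0 − 1.0) = 140,000.
- I vs D: (120 − 20) / (1.3 − 1.0) = 333,333. This exceeds P vs I, so I is extendedly dominated.
- Identity check: w = 0.3; 0.3 × 333,333 + 0.7 × 57,143 = 140,000.
- Net benefit at L = 100k: D = 100 − 20 = 80k; I = 130 − 120 = 10k; P = 200 − 160 = 40k. D is best value, yet P passes against I. The governing ICER is 140,000.

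**Case B: ipilimumab is good value.** D = 20k, 1.0; I = 60k, 2.0; P = 200k, 2.5.
- P vs I: (200 − 60) / 0.5 = 280,000.
- P vs D: (200 − 20) / 1.5 = 120,000.
- I vs D: (60 − 20) / 1.0 = 40,000. I is not dominated.
- Net benefit at L = 150k: D = 150 − 20 = 130k; I = 300 − 60 = 240k; P = 375 − 200 = 175k. I is best value, yet P passes against D. The governing ICER is 280,000.

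**Sensitivity to one input.** Case A, varying only ipilimumab QALYs:

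| Q_I | I vs D | P vs I | P vs D | I extendedly dominated? | Governing ICER for P |
|---|---|---|---|---|---|
| 1.1 | 1,000,000 | 44,444 | 140,000 | yes | 140,000 |
| 1.3 | 333,333 | 57,143 | 140,000 | yes | 140,000 |
| 1.5 | 200,000 | 80,000 | 140,000 | yes | 140,000 |
| 1.7 | 142,857 | 133,333 | 140,000 | yes | 140,000 |
| 1.8 | 125,000 | 200,000 | 140,000 | no | 200,000 |

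**Is the governing figure already planned?** If P has the most QALYs and the highest cost, NB_P ≥ NB_X exactly when L ≥ ICER(P vs X). P is best value only when this holds against both comparators, so its governing ICER is the larger of the two planned ratios: max(57,143; 140,000) = 140,000 in Case A and max(280,000; 120,000) = 280,000 in Case B. If P instead dominates I outright, P vs D governs, and it is also planned.

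**Acceptability curves.** Suppose separate curves give, at some threshold, probability a that P beats D and b that P beats I. The probability that P is the best of the three is then known only to lie between max(0, a + b − 1) and min(a, b). The two curves also say nothing about which of D and I is optimal when P is not. Curves drawn over all three options from the same simulation draws give these probabilities directly.

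**The case against.** The strongest reply is that nothing decision-relevant is missing. Both pairwise ICERs will be reported, and a reader who sees both can take the larger one whenever pembrolizumab has the most QALYs and the highest cost. Section 2.0 supports part of that ordering: it reports a better response rate than ipilimumab (34% against 12%) and better 12-month survival (74% against 58%). With QALYs ordered dacarbazine, ipilimumab, pembrolizumab, a ratio against ipilimumab below the ratio against dacarbazine is itself the sign that ipilimumab is extendedly dominated or, if that ratio is negative, that pembrolizumab dominates it outright. The model already covers all three treatments, so the missing comparison can be calculated at reporting. These are also secondary objectives in a trial that Section 14.2 calls exploratory.

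Most of this stands. A reader might infer that the plan could not detect an inefficient comparator, or that it would never produce the right ratio. The documents do not support that, because under the likely ordering the two planned ratios contain both the check and the answer. A reader might also infer that the acceptability curves will be pairwise. The text is silent, so this is a point to clarify and not an established fault.

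What the reply does not remove is the absence of a rule. The QALY and cost ordering is a result of the model, not something known now; the plan does not say the larger ratio governs; and separate acceptability curves, which the text allows, would not give the probability that each option is optimal.

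**Conclusion.** The point holds as a gap in the analysis rule and in how the conclusion will be drawn, not in the data. As written, either ratio could support a claim of cost-effectiveness, and the smaller one can pass a threshold at which pembrolizumab is not the best-value option. This can happen through the ipilimumab comparison (Case A) or the dacarbazine comparison (Case B).

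The size and direction cannot be determined from the documents. A reader might infer from an illustration that pembrolizumab's value would be overstated by some definite multiple. No such multiple is supported. In Case A the governing ratio is 140,000 / 57,143 = 2.4 times the flattering one. Changing only the assumed pembrolizumab cost from 160k to 130k gives (130 − 20) / 1.0 = 110k against (130 − 120) / 0.7 = 14.3k, or 7.7 times. Case B reverses which comparison flatters.

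The conclusion assumes that the three treatments are alternatives for the same first-line decision by the payer named in Section 14.4. The rule that the larger ratio governs also needs pembrolizumab to have the most QALYs and the highest cost. This is a cheap improvement, with no bearing on trial conduct or the primary texture objective.

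**What to change.** Add to Section 14.4, before results are available, that:
- the three strategies will be evaluated in the one Markov model and ranked by cost and QALYs;
- dominated and extendedly dominated strategies will be removed;
- the sequential (fully incremental) ICER is the base-case result and carries the conclusion, with both pairwise ICERs kept as supplementary results so that the two objectives in Section 1.2 are still met;
- the acceptability curves will show all three strategies jointly, using common parameter draws in the probabilistic analysis.

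The cost is a few lines of text and one extra results table. No new patients, visits or data are needed, because Section 14.4 already models costs and survival for all three treatments and sources utilities for both comparators. The downside for the sponsor is that the headline ICER may be less favourable than the smaller pairwise figure.
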